To evaluate the incidence of PFD symptoms among pregnant patients throughout their pregnancy, including the "4th trimester" postpartum period (or the 12 weeks following delivery) using validated Pelvic Floor Disability Index (PFDI-20).

3. Background

Pelvic floor disorders (PFDs) in females can occur in many phases of life some of which are better understood than others. Pregnancy and delivery have been well established as major risk factors for developing PFDs.¹ The American College of Obstetrics and Gynecologists (ACOG) has made a renewed effort to bring attention to many health issues women experience due to pregnancy and the postpartum period by focusing on the "fourth trimester", referring to the 12 weeks following delivery. In May of 2018, the ACOG committee opinion focused on redefining the postpartum visit. One of the areas described in the physical recovery is assessment of the perineum and the presence of PFDs such as fecal or urinary incontinence.² There are a wide variety of physical and mental health topics that need to be discussed in each perinatal visit and pelvic floor issues may not be addressed.

Prior studies have evaluated the information that patients receive during pregnancy and the most neglected area was educating patients on PFDs. Obstetricians cite their concern about patients developing PFDs in the future as a factor that they consider in their obstetric management during delivery.³ Patients are not well informed on their risk of developing PFDs and would be more equipped to participate in their care during pregnancy, during their delivery, and after pregnancy if they were better informed. Furthermore, many women have misconceptions about PFDs and are unaware of what their risks are and that there are prevention strategies and treatment options available to them.⁴ When patients have been asked about their perception of PFDs in one-on-one interviews, the findings suggested that younger women were less educated about PFDs while older women were more embarrassed to discuss these issues with others.⁵ The goal of this study is to investigate the best method for educating patients in the antepartum period and following them into the postpartum period to assess their retention of knowledge from the education they received.

Previous studies have examined this issue by various means of educating patients in different stages of the postpartum period. One such study examined immediate postpartum education on

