The obstetrics practice that we will be recruiting from has approximately 75 obstetrics patients per month. Assuming approximately 50% recruitment each month, we anticipate being able to complete recruitment in 6 months. We will start educational workshops once 10 patients are enrolled into the educational workshop arm of the study. In order to offer adequate availability to patients, we will plan to offer four workshops per month. As scheduling the workshops may pose a logistical challenge, we will assess patient availability and adjust timing of the workshops to maximize the number of patients at each workshop. We will continue to follow these patients through their pregnancy so the timeline of data collection will continue for approximately 9 months after the recruitment period ends. We estimate that data collection will be completed by August 2021.

2020			
July			
Aug			
Sept			
Oct			
Nov			
Dec			
2021			
Jan			
Feb			
Mar			
Apr			
May			
June			
July			
Aug			

Recruitment period

Educational workshops
four times per month

Data collection period will
continue until 3 months after the
completion of the intervention to
capture both questionnaire and
referral pattern data.

Inclusion criteria:

- Patients in the first or second trimester of pregnancy
- English speaking
- Greater than 18 years old

Exclusion criteria:

- Non-English speaking or unable to provide informed consent

5. Study Intervention

At the first research visit, patients will be consented and randomized. Patients may be approached regarding the study by phone. The research consent form will be sent to them via e-mail for them to review and they will sign the consent at their next in-person visit. They will complete the PIKQ and PFDI-20 questionnaires (Appendix A).^{8,9} After their baseline questionnaires are completed, they will receive written educational materials.

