Patients randomized into the written education group will only receive written materials. They will receive these materials at the first study visit and again when leaving the hospital after delivery. The written materials will consist of three one-page handouts with information on pelvic organ prolapse (POP), stress urinary incontinence (SUI), and pelvic floor exercises. These handouts will be created in collaboration with [name] and [name] who have experience in the study of patient's perceptions of PFDs and have collaborated with the American Urogynecology Society to create written educational materials in the past.⁴ We plan to seek feedback from patients regarding their impressions of our newly developed handouts prior to use.

The PFPT workshop group will both receive the written handouts and attend an in-person education workshop that will be led by a PFPT with approximately 5-10 study participants in each workshop. Patients will be allowed to attend the workshop after being randomized during pregnancy or during the postpartum period to maximize participation. The session will last approximately 1 hour and will review similar information to the content of the handouts. It will focus on educating the patients about pelvic floor anatomy, etiology of PFDs, prevention strategies, and informing them about urogynecologists and PFPTs. The educational workshops will be offered in either in person or virtual format to accommodate group gathering restrictions of COVID-19. The web-based meeting will be password protected and participants will have the option to share their video and do not have to provide their name as the participant if they do not want to. They have the option to verbally participate but this is not required.

Patients will be reassessed and complete the PIKQ and PFDI-20 questionnaires at their 6-week postpartum visit. We will also record delivery type. If patients do not attend their postpartum visit, they will be reached by phone or e-mail to complete the postpartum assessment. Referral patterns to PFPT and urogynecology will be assessed using electronic medical records during the study period and up to 3 months postpartum.

Patients from the workshop group will receive a follow up phone call to perform a brief phone survey on their perceptions of the two forms of educational materials: written versus workshop format. No medical information will be discussed in this phone call. Please see interview guide attached in appendix ***.

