6. Drugs, Biologics, Devices

No drugs, biologics, or devices will be used for this study.

7. Collaborative / Multi-site Research

This study will take place at one site within the Methodist system.

8. Data Privacy / Confidentiality

Houston Methodist policies for Protected Health Information (PHI) will be followed in access patient charts. PHI will be used to identify patients that are eligible for the study by reviewing clinical schedules. Patients will be assigned a subject ID number that is deidentified. There will be a master data sheet that will have patient MRNs associated with their subject ID number that is separate from the RedCap database. This data sheet will be stored on an encrypted password protected USB drive. No PHI will be disclosed. The data will be maintained for 6 years after the completion of the study and then destroyed.

The web based virtual workshop will not include the patient's personal information, including their name, unless they want to provide their name. They have the option to share their video or participate verbally in the workshop but it is not required. All participants will be muted and their video off on entry to the virtual meeting and they can choose to disable these features if desired. The virtual workshop meeting room will be password protected. This password will be provided to the participants via e-mail the day of the workshop. There will be a phone number to a study team member provided to them to call for any technical support if needed. None of the sessions will be recorded.

Identifier (or parts of)	Recorded	Disclosed	Comment
All elements of dates (except year) for dates directly related to an individual, including birth date, admission date, discharge date, date of death; and all ages over 89 and elements of dates (including year) indicative of such age	X		
Medical record numbers	X		
Phone number			Used for recruiting patients after virtual visits with their doctor.
Email address			Used to send questionnaires and consent forms if recruited virtually. Used to send password for virtual workshop.

9. Data and Specimen Banking

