Patient demographic data will be collected from the medical record and the PIKQ survey, including age, race, obstetrics history, marital status, household income, and education level. Delivery type will also be recorded at the 6 weeks postpartum visit. The patients will be asked to give responses to the PIKQ and PFDI-20 surveys. Data collected in the study will include referral patterns within the OBGYN group at Methodist to the urogynecology group and pelvic floor physical therapy group. The referral information will be collected for the 6 months

preceding the study and compared to the data collected during the study period. This data will be recorded on recruitment paperwork with a de-identified subject ID and recorded into a RedCap database.

10. Study Population

We will recruit female patients in the first or second trimester of pregnancy who are 18 years of age or older.

11. Screening and Recruitment^{SR}

Patients will be identified by reviewing the clinical schedule of the general obstetrics providers at Houston Methodist Hospital. The patients will be approached either in the waiting room prior to their appointment or while they are awaiting their physician visit in the clinic room. Patients may also be approached by phone after their visit with a physician if they are attending virtual visits. Recruitment flyers will be posted around the clinical area and waiting room of the Smith 2221 OBGYN clinical area.

12. Withdrawal of Subjects

Subjects may withdraw from the study at any time with no change to their routine obstetric care. Patients who experience a miscarriage or intrauterine fetal demise prior to viability will be withdrawn from participation.

13. Provisions to Protect the Privacy Interests of Subjects

Subjects will be required to provide minimal demographic information at their recruiting visit and this will not need to be repeated at any point. Their primary interaction with the research study team will be at recruitment, at the PFPT group workshop, and at their postpartum visit for the follow up questionnaire administration. The educational workshop will include females only and female PFPTs in small groups of 5-10 subjects. We plan to offer the workshops in either an in-person or virtual format to accommodate for current group gathering constraints due to COVID-19.

14. Risks to Subjects

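### The plan lets a workshop-arm woman attend after her own 6-week postpartum PIKQ; no rule puts the workshop before the primary assessment

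*Combined protocol and SAP*

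**What the plan says.** Section 5 (Study Intervention) sets the workshop timing: "Patients will be allowed to attend the workshop after being randomized during pregnancy or during the postpartum period to maximize participation". It gives no latest date. The only length the protocol attaches to this period is in the secondary aims of section 2: "postpartum period (or the 12 weeks following delivery".

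Section 5 fixes the follow-up assessment separately: "Patients will be reassessed and complete the PIKQ and PFDI-20 questionnaires at their 6-week postpartum visit". The fallback is: "If patients do not attend their postpartum visit, they will be reached by phone or e-mail to complete the postpartum assessment". The fallback has no window and is not linked to workshop attendance.

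Three places bear on the intended order:
- The Background (section 3) gives the goal as educating women before delivery and following them afterwards to see how much they retain.
- Section 13 lists the contacts with the study team as "at recruitment, at the PFPT group workshop, and at their postpartum visit for the follow up questionnaire administration".
- The Study Timeline in section 4 runs data collection until 3 months after the intervention is completed, for questionnaires and referrals.

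On scheduling, the Study Timeline says "we will plan to offer four workshops per month". The workshop arm also receives the handouts.

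**The concern.** The workshop is tied to randomisation and the PIKQ to delivery, and nothing ties the two to each other. On the 12-week description, the permission to attend reaches about 6 weeks past the primary assessment (12 − 6). A woman who completes the PIKQ at 6 weeks and attends at 8 weeks has followed the protocol. She nevertheless enters the primary comparison in the workshop arm having had handouts only.

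The hypothesis concerns women who attend a workshop. If some are tested first, the estimated difference mixes the effect of the workshop with the share who had not yet had it. A reader who sees a smaller difference than planned could not tell a weaker workshop from late attendance, because the plan does not ask for the order to be recorded or reported.

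**Working it through.** **1. Is there a rule for each woman?** The permission in section 5 allows a session after the PIKQ. The retention goal in section 3 presupposes education first, but it is an aim. The list in section 13 describes contacts within a privacy section. The timeline in section 4 is set for the study as a whole, and a woman tested at week 6 who attends at week 8 still fits it. None of the three sets a deadline for an individual, and no passage says how a woman tested first is to be handled.

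**2. Would the order be known afterwards?** The data items in section 9 do not include workshop attendance or its date. The identifier table in section 8 marks "All elements of dates (except year) for dates directly related to an individual" as recorded, but it is a general checklist and does not mention the workshop. Parking is to be paid for the dates of attendance (section 15), but no record by subject is described. For virtual sessions names are optional, and of the meeting password section 8 says "This password will be provided to the participants via e-mail the day of the workshop", which identifies those invited and not those who joined. The follow-up call to the workshop group (section 5) might capture attendance, but its guide is not shown.

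**3. The plan's own sample size.** Section 4 assumes 0.45 at baseline, rising to 0.80 (workshop) and 0.54 (written), and needs 96 women for 80% power at two-sided 0.05. The two-proportion formula with unpooled variance gives (0.80×0.20 + 0.54×0.46) × (1.960 + 0.842)² / 0.26² = 47.4, so 48 per group and 96 in all. Allowing for 20% dropout, 96/0.80 = 120. Both figures match the plan. The pooled formula, which is the one the plan names, gives 51 per group; at 48 per group its power is 78.2%.

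**4. Dilution.** The planned primary comparison is a two-sample test on change scores. The planned difference in change is (0.80 − 0.45) − (0.54 − 0.45) = 0.26, or 24 × 0.26 = 6.24 PIKQ points. Let f be the share of workshop-arm women tested before their workshop, and assume that they score like the written arm. Then:
- difference = 0.26 × (1 − f)
- written-arm variance = SD²
- workshop-arm variance = SD² + f(1 − f) × 0.26²
- power from the noncentral t distribution, 48 per group, two-sided 0.05

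Example with f = 0.20 and SD = 0.30: the difference is 0.208; the workshop variance is 0.0900 + 0.16 × 0.0676 = 0.1008; the standard error is √((0.0900 + 0.1008)/48) = 0.0630; the noncentrality is 0.208/0.0630 = 3.30; power is 0.904.

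| f | Women of 48 | Difference | Points of 24 | Power, SD 0.30 | Power, SD 0.35 |
|---|---|---|---|---|---|
| 0 | 0 | 0.260 | 6.24 | 0.988 | 0.950 |
| 10% | 4.8 | 0.234 | 5.62 | 0.961 | 0.893 |
| 20% | 9.6 | 0.208 | 4.99 | 0.904 | 0.805 |
| 30% | 14.4 | 0.182 | 4.37 | 0.808 | 0.688 |

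At SD 0.20 and 0.25, power at f = 30% is 0.982 and 0.917. The documents give neither f nor an SD.

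**5. How large could f be?** Four workshops a month is 48 a year. Assume late entry at 27 weeks and delivery at 37 to 40 weeks. The time to a 6-week PIKQ is then (37 − 27) + 6 = 16 to (40 − 27) + 6 = 19 weeks, which holds 16 × 48/52 = 14.8 to 19 × 48/52 = 17.5 workshops. To be tested first, such a woman would have to miss all of them. Women who enter earlier have more chances.

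**The case against.** The strongest reply is that the order is plain enough. The retention goal, the list of contacts and the timeline all point the same way. Sections 5 and 13 do not contradict each other, since attendance between delivery and the 6-week visit satisfies both. The flexibility is deliberate: section 5 gives participation as its reason, and section 15 names attendance as a known difficulty. A deadline would also relabel some late attenders as non-attenders without changing their scores. Women who never attend leave a reader with much the same ambiguity.

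Most of this stands. The intended order is clear, the text needs clarifying rather than correcting, and the benefit of a deadline is limited. But intent shown in descriptive text does not bind the individual woman, and the express permission in section 5 goes past the assessment.

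Three stronger readings should be resisted.
- A reader might infer that the gap can only pull the difference toward zero and can never favour the workshop. That needs women tested first to score like the written arm. Equal exposure is not established: section 5 states a second set of handouts at discharge for the written group only. The same open timing also permits attendance just before the PIKQ, which could raise scores relative to a retention aim.
- A reader might infer that in-person order is recoverable and only virtual sessions are in doubt. The checklist and the parking payments do not show that. Nor do optional names show that the study team keeps no virtual attendance record.
- A reader might infer a serious loss of power from the sample-size model, where power at 48 per group falls from 78.2% to 56.8% at f = 20%. That model treats a mean score as a proportion and is not the planned test.

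**Conclusion.** The concern holds as a gap in wording: the stated permission lets the workshop follow the primary endpoint, and no passage says that attendance or its date is recorded by subject in either format. This much follows from the text alone.

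The size does not. At f = 10% the planned 6.24 points would become 5.62, and at 30% they would become 4.37, provided that women tested first score like the written arm. Power stays above 80% up to f = 30% at an SD of 0.30, but falls to 0.688 at 0.35, so whether power matters depends on an SD that the documents do not give. A large f looks unlikely on the workshop schedule, and no material harm is shown. The main cost is to interpretation of a smaller-than-planned difference. Severity is minor; this is a cheap improvement.

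**What to change.** Clarify section 5 in one sentence: the study workshop is to be completed before that woman's own follow-up PIKQ, whether that is done at the 6-week visit or later by phone or e-mail. Postpartum attendance up to that point remains allowed.

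Record workshop attendance and date (in person and virtual) and the PIKQ date by subject ID. A virtual log kept by subject ID needs no name shown in the meeting. Keep every woman in her randomised arm whether or not she attended. Report the number with no workshop before the PIKQ and the interval from workshop to PIKQ.

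The cost is one sentence, two dates per woman and an attendance log. The downside is that women who can attend only late count as non-attenders, and dilution falls only as far as the deadline brings attendance forward. Attendance shortly before the PIKQ becomes visible but is not prevented.

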Patients' baseline characteristics will be summarized according to the two groups. All data will be presented as mean \pm SD or median (interquartile range) for continuous variables, and number (percentage) for categorical variables. Chi-squared or Fisher's exact test (categorical variables) and Student's t-test or Mann-Whitney test (continuous variables) will be used to compare patients between PFPT and written education group at baseline. Paired t-test or Wilcoxon signed-rank test will be used to compare questionnaire scores between baseline and the follow-ups within each group. Student's t-test or Mann-Whitney test will be used to compare the paired difference between the two groups. The Shapiro-Wilk test will be used to check the normality. Pearson's correlation coefficient or Spearman's rank correlation coefficient will be used to analyze the relationships among variables. All analyses will be performed with STATA version 16 (StataCorp. 2019. Stata Statistical Software: Release 16. College Station, TX: StataCorp LLC). Statistical significance will be defined as two-tailed $p < 0.05$ for all tests.

Sample Size Calculation:

Our primary objective of the proposed study is to evaluate the hypothesis that patients attending an educational workshop from PFPTs will have improved knowledge of pelvic floor disorders (PFDs) as measured by the Prolapse and Incontinence Knowledge Questionnaire (PIKQ) as compared to patients in the written education group. We will use the 24-point PIKQ questionnaire composite score as our primary endpoint. Based on the PIKQ validation study, a composite score of 0.45 (45%) is expected in women of this age at baseline.⁸ Assuming in our study population at baseline a score of 0.45, we would expect an increase in the composite

score to 0.8 in the PFPT group and an increase in composite score to 0.54 in the written education group. Therefore, a sample size of 96 patients will be needed to detect the difference with 80% power and a significance level of 0.05 based on the two-sided Z-test with pooled variance. After considering 20% dropout rate from the study, the total sample size will be 120 patients (60 per group). PASS 2015 (PASS 15 Power Analysis and Sample Size Software (2017). NCSS, LLC. Kaysville, Utah, USA, ncss.com/software/pass) was used for sample size calculation.

Study Timeline:

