There are minimal risks associated with this study. The cost of parking in the medical center may pose a burden to some subjects and so we plan to compensate the cost of parking to try to offset this. Otherwise, there is no physical, social, legal, or psychological risk to the subjects.

15. Potential Benefits

Regardless of the group to which the subjects are randomized, they will be given education on PFDs that they would not typically receive in their routine obstetric care. This may provide the opportunity to make subjects aware of treatment options for PFDs that they were not aware of and provide them an opportunity to improve their quality of life.

A potential challenge would be ensuring that patients receive their follow up assessment as patients may not show up for their postpartum visit. A strategy to improve follow up would be to consent patients to the option of receiving and completing the PIKQ and PFDI-20 by e-mail if they do not attend their postpartum visit. Another potential challenge may be ensuring that patients attend their assigned group workshop. A strategy to improve attendance and

enrollment would be to compensate patients. We plan to compensate their parking on the dates that they attend the group workshop.

16. Financial and Economic Issues

The only cost to the study subjects will be the cost of parking to attend the group workshop. The remainder of the study visits will occur at the same time as routine care visits. We will plan to compensate the cost of parking at the time of their group workshop with an estimated cost of \$960 (\$16 per participant).

17. Data Safety Plan

Please see above description of Data and Specimen Banking.

18. Informed Consent Documentation and Process

Informed consent will be obtained prior to any of the study procedures with the attached informed consent template. Consent will be obtained from a member of the research team. The consent document may be e-mailed to participants after being recruited by phone for their review. They will then sign the consent form at their next in-person physician visit.

19. Waiver of Informed Consent and /or Authorization

A screening waiver will be requested preparatory for research (waiver requested for feasibility, recruiting, access to charts, pre-screening). We are not requesting a waiver of informed consent.

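### The primary knowledge test may be completed unsupervised by e-mail, with no answer-from-memory instruction, no record of completion mode and no analysis by mode

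*Combined protocol and SAP*

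**What the plan says.** The sample-size text in section 4 fixes the endpoint: "We will use the 24-point PIKQ questionnaire composite score as our primary endpoint". Section 3 gives the purpose of following women after delivery: "to assess their retention of knowledge from the education they received". The PIKQ in Appendix A is a set of statements to be marked agree, disagree or don't know.

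Follow-up testing is planned for the 6-week postpartum visit. For those who miss it, section 5 says: "If patients do not attend their postpartum visit, they will be reached by phone or e-mail to complete the postpartum assessment". Section 15 treats missed visits as a foreseeable difficulty and proposes consenting women to "receiving and completing the PIKQ and PFDI-20 by e-mail if they do not attend their postpartum visit". The two remote routes are not ranked.

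Under section 5 both arms receive handouts on prolapse, stress incontinence and pelvic floor exercises, given out after the baseline questionnaires. A second supply at hospital discharge is described for the written arm.

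The section 8 identifier table adds that e-mail addresses are "Used to send questionnaires and consent forms if recruited virtually". Sections 5 and 18 have women approached by phone sign consent at their next in-person visit, and section 18 puts consent before any study procedure.

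The between-arm analysis in section 4 is a t-test or Mann-Whitney test on change scores. In the text as it can be read, nothing asks for answers from memory, records completion mode or analyses by mode.

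**The concern.** For a symptom scale, where the form is filled in matters less. For a knowledge test it can change what is measured. A woman answering an e-mailed quiz can consult the handouts or the internet, and her score may then show access to information rather than retention. The plan pools such scores with clinic and phone scores as if they were the same measurement.

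Completion mode follows visit attendance, which happens after randomisation and may differ by arm. If mode is not recorded at the time, nobody can later tell whether look-up affected the primary comparison, or in which direction. What is at stake is mainly the size and meaning of the estimated difference.

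**Working it through.** **The plan's own figures.** The sample-size text starts from 0.45 at baseline and gives the expected follow-up values as "score to 0.8 in the PFPT group and an increase in composite score to 0.54 in the written education group". On the number required it says: "a sample size of 96 patients will be needed to detect the difference with 80% power and a significance level of 0.05". It names a two-sided Z-test and describes the variance as pooled.

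- Expected gap: 0.80 - 0.54 = 0.26, or 0.26 x 24 = 6.24 points.
- Treating the scores as two proportions with unpooled variance: n = (1.960 + 0.842)^2 x (0.80 x 0.20 + 0.54 x 0.46) / 0.26^2 = 47.4, so 48 per arm and 96 in total. With 20% dropout, 96 / 0.8 = 120. Both figures reproduce. (The pooled formula gives 51 per arm, 102 in total. That is a separate matter and nothing here depends on it.)

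**Similar e-mail use in both arms.** Let f be the fraction of women, equal in both arms, who miss the visit, answer by e-mail, look answers up and then reach a common score c. The gap is

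[0.80(1 - f) + cf] - [0.54(1 - f) + cf] = 0.26 x (1 - f).

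The value of c cancels. The documents give no f, so these are illustrations:

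| f (assumed) | gap | points of 24 |
|---|---|---|
| 0% | 0.260 | 6.2 |
| 3% | 0.252 | 6.1 |
| 10% | 0.234 | 5.6 |
| 20% | 0.208 | 5.0 |

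Because f is a joint event, it can be small. For example, 20% missing the visit x 50% of those using e-mail x 30% of those looking up = 3% (all three assumed).

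**Unequal use.** Let fW and fP be the look-up fractions in the written and workshop arms, and assume a look-up score of 0.90. The gap is [0.80(1 - fP) + 0.90 fP] - [0.54(1 - fW) + 0.90 fW].

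- fW = 40%, fP = 20%: 0.820 - 0.684 = 0.136.
- fW = 20%, fP = 40%: 0.840 - 0.612 = 0.228.
- fW = 0%, fP = 40%: 0.840 - 0.540 = 0.300, larger than 0.26.

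These shares are deliberately large, to show that the sign of the bias is not fixed.

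**Power, 48 per arm.** On the plan's proportion model (unpooled, workshop arm held at 0.80, written arm raised), power is 80.5% with no dilution, 72% at f = 10% and 62% at f = 20%. The planned test compares mean changes, and the documents give no SD. With an assumed SD of 0.20 to 0.30, power at a gap of 0.208 is 99.9% to 92%.

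**Baseline.** Handouts come only after the baseline questionnaires, so look-up at that point could use only outside sources such as the web. Neither arm has been taught anything yet, so any such look-up is expected to be equal across arms and to cancel in the comparison of change scores. It could shrink the change within each arm.

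**The case against.** The e-mail route exists to protect follow-up in a trial that already allows for 20% dropout, and missing primary data would be a real cost. Only women who miss the visit are exposed, some of them will be reached by phone, and no share is documented. That handouts are kept at home and consulted is an inference. No passage says that clinic completion is supervised either. All of this stands. It limits the size of the problem but does not supply the missing instruction or record.

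A reader might infer several stronger things that the documents do not support:

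- **That an e-mailed PIKQ is an open-book test.** It can be; nothing shows that it will be.
- **That look-up must shrink the difference.** This needs similar e-mail use in both arms.
- **That baseline look-up biases the primary contrast.** The order of baseline testing and handouts in section 5 argues against it. The section 8 entry on e-mailed questionnaires does not say which questionnaire or when, so it is an ambiguity to reconcile.
- **That phone should replace e-mail.** A call introduces an interviewer, and the documents describe no blinding, so this is a trade-off.

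Excluding e-mail completions also selects on behaviour after randomisation, so that analysis cannot cleanly isolate the effect of mode.

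**Conclusion.** The point holds as a gap in how the primary outcome is measured. A test of retained knowledge may be completed unsupervised by e-mail by women in either arm who have been given handouts on its subject, and the plan would neither discourage look-up nor allow it to be detected.

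Under similar e-mail use, with look-up bringing the affected women to the same score in both arms, the loss is 0.26 x f: about 0.008 at f = 3% and 0.026 at f = 10%. Under unequal use the direction is unknown. These sizes rest on assumed values of f and on the plan's expected scores. A changed trial conclusion is not shown; on a mean-score model with the assumed SDs, power stays at 92% or more even at f = 20%. The case for acting is that the bias is avoidable, would be invisible in the data as planned, and costs very little to address.

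**What to change.** - **Section 5 and Appendix A:** print on every PIKQ, in all modes and at both time points: *Please answer from memory without using handouts or the internet.*
- **Data collection:** record the mode of each PIKQ (clinic, phone, e-mail) in RedCap, and report mode by arm.
- **Statistical Analysis (section 4):** add a sensitivity analysis of the primary comparison excluding e-mail completions, labelled in advance as non-randomised and supportive only.
- **Fallback routes:** keep e-mail so that follow-up is protected. Where phone is used, read the items verbatim without prompting.
- **Baseline:** reconcile the section 8 entry on e-mailed questionnaires with sections 5 and 18, so that no baseline PIKQ is completed before consent is signed.

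The cost is one instruction line, one data field, one supportive analysis and a clarifying edit. No patients or visits are added. The instruction cannot guarantee compliance, but recording mode makes any remaining problem visible.
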